8.2.3 Visit 2 (dosing visit)

Visit 2 will take place on Day -1 to Day 1.

The subjects will attend the clinical center the day prior to dosing (Day -1) and subject eligibility is rechecked (check of changes between the screening visit and Visit 2) and those subjects eligible to participate should stay onsite overnight. To target a glucose level around 90-110 mg/dL (5.0-6.1 mmol/L) the following morning, subjects may be administered insulin glulisine (Apidra[®]) at the investigator's discretion either by IV infusion, SC bolus or continuous SC insulin infusion. Dosing will take place the following morning (Day 1).

On Day 1 and prior to the start of the insulin-induced hypoglycemic procedure, those subjects eligible to participate will be randomized to treatment with dasiglucagon, placebo, or GlucaGen.

The following assessments will also take place:

- Document all changes in concomitant medication (prior to the start of the insulin-induced hypoglycemic procedure)
- Check of withdrawal criteria (prior to the start of the insulin-induced hypoglycemic procedure)
- Check of dosing day exclusion criteria (prior to the start of the insulin-induced hypoglycemic procedure)
- Vital signs (prior to the start [within 30 minutes] of the insulin-induced hypoglycemic procedure, and at 30, 90 and 300 minutes after dosing). 12-lead ECG (prior to the start [within 30 minutes] of the insulin-induced hypoglycemic procedure, and at 20, 35, 45, 60, and 300 minutes after dosing)
- Local tolerability (at 30, 120, and 300 minutes after dosing)
- AEs
- Biochemistry, hematology (prior to the start of the insulin-induced hypoglycemic procedure [within 30 minutes], and at 30 and 300 minutes after dosing)
- Urine stick pregnancy test (women of childbearing potential only; prior to the start of the insulin-induced hypoglycemic procedure)
- Urinalysis (prior to the start of the insulin-induced hypoglycemic procedure [within 120 minutes])
- Urine drug screen (prior to the start of the insulin-induced hypoglycemic procedure)
- Alcohol breath test (prior to the start of the insulin-induced hypoglycemic procedure)

- Dasiglucagon/GlucaGen plasma concentrations:
 - Pre-dose, 15, 30, 35, 40, 50, 60, 90, and 120 minutes after dosing. The actual time of blood sampling for exposure should not deviate from the nominal time by more than ± 1 minute. Pre-dose is defined as within 2 minutes prior to dosing.
- Plasma glucose concentrations:
 - Pre-dose, 4, 6, 8, 10, 12, 15, 17, 20, 25, 30, 40, 50, 60, 75, and 90 minutes after dosing. The actual time for blood sampling for plasma glucose should not deviate from the nominal time by more than ± 30 seconds until the 20 minute collection time point and by more than ± 1 minute for the subsequent collection time points. Pre-dose is defined as within 2 minutes prior to dosing.
- Antibodies against dasiglucagon/GlucaGen (prior to the start of the insulin-induced hypoglycemic procedure).
- Plasma insulin concentrations:
 - Pre-dose, 30 and 60 minutes after dosing. The actual time of blood sampling for plasma insulin should not deviate from the nominal time by more than ± 1 minute. Pre-dose is defined as within 2 minutes prior to dosing.

8.2.3.1 Hypoglycemic clamp procedure and administration of trial medication

The following procedure is based on precented procedures for hypoglycemia induction in patients with T1DM [24, 25].

The treatment day (Visit 2, Day 1) will be conducted after an overnight fast, targeting a starting plasma glucose around 90 to 110 mg/dL (5.0-6.1 mmol/L).

Subjects who meet one or more of the dosing day exclusion criteria (Section 5.5) at the dosing visit will be excluded from the dosing visit, but the visit can be rescheduled 1-7 days later. The dosing visit can only be rescheduled once.

The subject's current insulin therapy will be washed out as defined in Section 5.5. For subjects using multiple daily injections, the date, time and the dose of the last basal insulin and the last short-acting insulin (except insulin glulisine [Apidra[®]]) administration prior to dosing will be captured. For subjects using an insulin pump, the time of discontinuation of the basal rate will be captured. Any use of insulin glulisine (Apidra[®]) in the last 5 hours prior to initiation of the hypoglycemia induction procedure will also be captured.

At approximately 08:00 hours, an infusion catheter will be inserted into each arm (forearm cephalic vein) for the manual glucose clamp procedure, with the glucose infusion in one arm and the insulin infusion in the opposite arm (if IV insulin glulisine [Apidra[®]] has been administered during the night the same infusion catheter can be used). A third catheter for blood sampling will be placed into a metacarpel vein for blood

sampling. This hand will be warmed (55-65°C) to arterialize venous blood. If there are issues with blood sampling from the metacarpal vein for the purpose of glucose measurements, a new and more proximal IV access may be used at the discretion of the investigator.

Hypoglycemia will be gradually induced by a fast-acting IV insulin glulisine (Apidra®) infusion (15 U [100 U/mL] in 49 mL saline and 1 mL of subject's blood or plasma), initially at 150% of the subject's usual basal rate and can be increased or decreased over a range of 0% to 200% or more as judged necessary by the investigator, to achieve a controlled decline in plasma glucose, targeting a plasma glucose level of 55 mg/dL (3.1 mmol/L).

Plasma glucose concentrations will be measured using the US FDA-approved glucose analyzer YSI 2300, Yellow Springs Instruments, Yellow Springs, OH or the Super GL analyzer, [name] GmbH, Freital, Germany. After the start of the insulin infusion, plasma glucose will be measured approximately every 10 minutes while plasma glucose is above 110 mg/dL, and approximately every 5 minutes once plasma glucose is at or below 110 mg/dL.

Once the glucose concentration declines to <60 mg/dL (3.3 mmol/L), the insulin infusion will be stopped, and 5 min later plasma glucose concentration will be measured at the glucose analyzer and blood samples for baseline assessment of plasma glucose, dasiglucagon/GlucaGen PK, and insulin PK will be collected. The samples are the baseline samples and should be collected within 2 minutes before IMP administration.

- If plasma glucose is ≥ 45 mg/dL and < 60 mg/dL (2.5-3.3 mmol/L), study treatment (IMP) will be administered, defining time, $t=0$. The study treatment will be delivered in the abdomen, buttock, or thigh (according to stratification) via SC injection.
- If plasma glucose is < 45 mg/dL (2.5 mmol/L), IV glucose solution will be administered sufficient to raise plasma glucose to within the 45-60 mg/dL target range. The run-in period will be adequately extended (at least 30 min) until the above target is achieved and new baseline samples for plasma glucose, dasiglucagon/GlucaGen PK, and insulin PK will be collected. Glucose should not be infused within 10 minutes before IMP administration. If plasma glucose is not within target range after the second attempt, the subject should be rescheduled for a new treatment visit within 7 days (+ 2 days).

Administration of IMP should not occur earlier than 9:00 hours in the morning or later than 12:00 hours.

As shown in **Table 4**, serial blood samples for glucose will be collected at $t=0, 4, 6, 8, 10, 12, 15, 17, 20, 25, 30, 40, 50, 60, 75$ and 90 minutes post-dosing. Samples for assessing

plasma dasiglucagon/GlucaGen concentration will be collected at t=0, 15, 30, 35, 40, 50, 60, 90, and 120 minutes. Samples for assessing plasma insulin concentration will be collected at t=0, 30, and 60 minutes.

Table 4 Post-treatment blood sampling times

Times	0	4	6	8	10	12	15	17	20	25	30	35	40	50	60	75	90	120
Plasma glucose	Y	Y	Y	Y	Y	Y	Y	Y	Y	Y		Y	Y	Y	Y	Y	Y	
PK Dasiglucagon/ GlucaGen	Y						Y				Y	Y	Y	Y	Y		Y	Y
PK Insulin	Y										Y			Y				

Refer to Section [7.2.7](#) for details of laboratory safety sampling and to Section [7.4.2](#) for details of blood glucose safety sampling.

When the t=90-minute blood sampling for plasma glucose has been collected the subjects are allowed to eat moderately. Drinking of water is allowed *ad libitum* during the entire procedure.

Hypoglycemia Rescue Provisions

During insulin-induced hypoglycemia, plasma glucose levels will be monitored closely at site for safety reasons as described in Section [7.4.2](#). Subjects should receive post-treatment rescue glucose infusion to ameliorate persistent hypoglycemia, as follows.

1. Glucose infusion should be initiated if a subject experiences severe alarming escalation of symptoms of hypoglycemia (e.g. symptoms suggesting a change in consciousness) at any time during the trial; glucose infusion should be initiated targeting a plasma glucose levels >70 mg/dL.
2. If plasma glucose is <45 mg/dL (2.5 mmol/L) between t=8 and t=44 minutes, rescue glucose infusion (1-2 mg/kg administered IV over about 5 seconds) should be initiated to maintain plasma glucose between 45 mg/dL and 55 mg/dL (2.5-3.1 mmol/L). Pause glucose infusion if plasma glucose is >55 mg/dL.
3. If plasma glucose is <70 mg/dL at t=45 minutes, rescue glucose infusion (2-3 mg/kg administered IV over about 5 seconds) should be initiated to maintain plasma glucose between 70 mg/dL and 80 mg/dL (3.9-4.4 mmol/L). Pause glucose infusion if plasma glucose is >75 mg/dL (4.2 mmol/L).

Subjects should remain in bed until completion of the test procedure 300 minutes after dosing (bathroom visits are allowed).

The IMP will be administered SC according to Section 6.3. The time of IMP administration will be recorded. At the timepoint when the insulin infusion is stopped, the total insulin dose which was required to induce hypoglycemia will be recorded.

AEs will be specifically recorded during the procedure at several timepoints.

The investigator must provide information to the subjects on how to resume their usual diabetes treatment.

The subject may be released from the clinical center if the investigator does not have any safety concerns based on the last safety plasma glucose value and the general condition of the subject. However, at the discretion of the investigator or on request of the subject, the subject may stay at the trial center for a longer period.

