7.4 Other assessments

7.4.1 Immunogenicity

Antibodies against dasiglucagon/GlucaGen will be measured at the dosing visit (Visit 2) and at follow-up (Visit 3). At the dosing visit (Visit 2), samples will be collected prior to the start of the insulin-induced hypoglycemic procedure.

The clinical ADA assays, specific for dasiglucagon and GlucaGen, respectively, have been validated in accordance with existing guidelines and recommendations ([17-21](#)).

Confirmed positive anti-dasiglucagon antibody samples (treatment-induced or treatment-boosted) from anti-dasiglucagon antibody-positive subjects will be evaluated for binding titer neutralizing potential and titer as well as cross-reactivity towards endogenous glucagon.

No further serum sampling will be needed as the ADA samples can be used for neutralizing antibody analysis.

The in vitro neutralizing effect of the antibodies will be measured using an assay based on glucagon receptor transfected human embryonic kidney cells ([20,22](#)). The calculated sensitivity in previous studies was about 51.8 ng/mL. The assay was also validated for recombinant glucagon with similar results ([21,23](#)). In case of a positive result in the neutralizing antibody assay, a titer estimation will be performed. The cell-based neutralizing antibody analyses will be performed by a special laboratory, BioAgilytix, Durham, NC, USA.

Residual and additional antibody serum samples may be stored until approval of market authorization by the health authorities. Further characterization of the antibody response may be requested by the health authorities.

7.4.2 *Plasma glucose measurements for safety*

During insulin-induced hypoglycemia, plasma glucose levels will be monitored closely at site. After the start of insulin infusion, plasma glucose should be checked approximately every 10 minutes while plasma glucose is above 110 mg/dL, and approximately every 5 minutes once plasma glucose is at or below 110 mg/dL and until after dosing when the subject's plasma glucose is ≥ 70 mg/dL (3.9 mmol/L). Hereafter, plasma glucose should be checked approximately every 30 minutes until 300 minutes (5 hours) after dosing. Plasma glucose concentrations will be measured using the US FDA-approved glucose analyzer YSI 2300, Yellow Springs Instruments, Yellow Springs, OH or the Super GL analyzer, [name] GmbH, Freital, Germany.

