At the discretion of the investigator, additional plasma glucose measurements can be taken at any time during the trial, for example when there is a suspicion (e.g. symptoms) of a hypoglycemic episode.

Plasma glucose measurements for safety should only be recorded in the eCRF if they are related to an AE (e.g. a hypoglycemic episode).

In case of persistent post-treatment hypoglycemia, subjects will receive rescue treatment with an IV glucose infusion (see Section 8.2.3.1 for details). Blood samples for PD and PK assessments should still be taken at the specified timepoints.

7.4.3 *Plasma insulin measurements*

Samples for insulin assessment will be collected at the dosing visit (Visit 2, pre-dose and at 30 and 60 minutes after dosing). The actual time of blood sampling for evaluation of plasma insulin should not deviate from the nominal time by more than ± 1 minute. Pre-dose is defined as within 2 minutes prior to dosing.

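### Rescue items 2 and 3 order an infusion that holds a glucose range, but dose it only as a 5-second push; item 3's range also falls where scheduled checks drop to about every 30 minutes

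*Protocol*

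**What the plan says.** The Hypoglycemia Rescue Provisions in Protocol Section 8.2.3.1 have three items. Item 1 covers alarming symptoms at any time; it targets glucose above 70 mg/dL and fixes no dose. Items 2 and 3 are triggered by a glucose value.

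- Item 2 (below 45 mg/dL, 8 to 44 minutes): "rescue glucose infusion (1-2 mg/kg administered IV over about 5 seconds) should be initiated to maintain plasma glucose between 45 mg/dL and 55 mg/dL". Glucose is paused above 55 mg/dL.
- Item 3 (below 70 mg/dL at 45 minutes): "rescue glucose infusion (2-3 mg/kg administered IV over about 5 seconds) should be initiated to maintain plasma glucose between 70 mg/dL and 80 mg/dL". The stop rule is "Pause glucose infusion if plasma glucose is >75 mg/dL".

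Before dosing, the same section handles a value below 45 mg/dL differently: "IV glucose solution will be administered sufficient to raise plasma glucose to within the 45-60 mg/dL target range". That rule is tied to its target and fixes no dose.

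Section 7.4.2 sets the bedside checks: "approximately every 5 minutes once plasma glucose is at or below 110 mg/dL and until after dosing", when glucose has reached at least 70 mg/dL. Then: "Hereafter, plasma glucose should be checked approximately every 30 minutes until 300 minutes". It also allows that "At the discretion of the investigator, additional plasma glucose measurements can be taken at any time during the trial". For the rescue itself, Section 7.4.2 refers back to Section 8.2.3.1. Section 7.2.2 repeats the triggers without a dose.

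**The concern.** Two parts of the rescue instruction do not fit together.

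1. **Dose and target.** Holding a range and pausing above a limit describe a continuing or repeated delivery. The bracket describes one push that is over in about 5 seconds. Nothing says what follows it.
2. **Range and monitoring.** All of item 3's range lies at or above 70 mg/dL, the level at which scheduled checks become about six times less frequent.

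The subjects have been made hypoglycemic on purpose, and those on placebo have no active drug to raise their glucose. At stake are how well a rescued subject is brought up and kept up, whether the 4 to 6 sites do the same thing, and what the descriptive amount of glucose infused (Synopsis, safety analyses) would represent. Rescue dosing is clinical procedure, so a statistical analysis plan would not be expected to supply it.

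**Working it through.** The protocol gives no figure to reproduce here. The check is direct arithmetic on the stated doses, followed by a comparison of sections.

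**Inputs from the protocol**
- Item 2: 1-2 mg/kg per push, range 45-55, pause above 55 mg/dL (Section 8.2.3.1).
- Item 3: 2-3 mg/kg per push, range 70-80, pause above 75 mg/dL (Section 8.2.3.1).
- Checks: about every 5 minutes until at least 70 mg/dL after dosing, then about every 30 minutes (Section 7.4.2).

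**Assumptions not in the protocol**
- Glucose distribution volume 1.5-2.5 dL/kg. As an extreme bound, plasma only: 0.45 dL/kg.
- Glucose uptake and endogenous recovery are ignored.

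**Step 1: rise from one push = dose / volume**
- Item 2: 1/2.5 = 0.4 to 2/1.5 = 1.3 mg/dL.
- Item 3: 2/2.5 = 0.8 to 3/1.5 = 2.0 mg/dL.
- Item 3, plasma-only bound: at most 3/0.45 = 6.7 mg/dL.

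**Step 2: the hand-over from item 2 to item 3**
- A subject kept at 45-55 mg/dL needs 70 - 55 = 15 to 70 - 45 = 25 mg/dL to reach item 3's lower limit.
- One item 3 push from 55 reaches at most 55 + 2.0 = 57.0 mg/dL, or 55 + 6.7 = 61.7 mg/dL on the plasma-only bound.
- Even on that bound the push covers 6.7/15 = 0.44 of the smallest gap.

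**Step 3: why a repeat interval matters**
- If item 3 pushes were repeated every 5 minutes, delivery would average 2/5 = 0.4 to 3/5 = 0.6 mg/kg/min.
- If repeated every 30 minutes, it would average 2/30 = 0.07 to 3/30 = 0.10 mg/kg/min.
- The two differ sixfold, and the protocol does not choose between them. This is an illustration, not a regimen that the protocol states.

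**Step 4: item 3 against the check schedule**
- The lower limit (70), the pause limit (75) and the upper limit (80) are all at or above 70 mg/dL, so all fall in the 30-minute schedule.
- Section 7.4.2 does not say whether the 5-minute checks resume if glucose drops below 70 again.
- The efficacy samples at 50, 60, 75 and 90 minutes do not fill the gap, because Section 7.1.1 has them sent to the clinical laboratory.
- Extra bedside checks are permitted but not required.

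**Step 5: reach into the efficacy analyses**
- Section 9.5.2.1 sets any rescued subject to not recovered at 45 minutes, whatever amount was given.
- Recovery within 10 to 30 minutes requires no rescue, and Section 9.5.3.1 carries forward the change from baseline at rescue in subjects rescued before recovery. Neither depends on the amount.
- The triggers, and so the time to first rescue, do not depend on what is given afterwards.
- For the sensitivity analysis without censoring for rescue: recovery needs at least 45 + 20 = 65 mg/dL. One item 2 push at 55 gives 55 + 1.3 = 56.3, or 55 + 2/0.45 = 59.4 mg/dL on the plasma-only bound. Both are below 65.

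**The case against.** The best defence is that Section 8.2.3.1 describes a manual clamp with its own glucose line, so the bracket can be read as a starting dose, with the range and pause limit governing what follows. The pre-dose rule states no rate either, and insulin titration is also left to the investigator. That reading is workable, and a trained site would probably adopt it. But the text does not state it, and Section 10.9 tells sites to keep to the protocol to the letter.

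A second defence is that the two halves pull apart. If pushes are small, overshooting 75 mg/dL between checks is hardly a risk; if glucose runs continuously, the shortfall arithmetic does not apply. This is fair about overshoot. But the range also has a lower end, and a fall below 70 between 30-minute checks can be missed on either reading.

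A reader might infer more in three ways, none of which the documents support.

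- **A long delay to 70 mg/dL.** One push per 5-minute check, starting at 45-55 mg/dL, would take 15/2.0 = 7.5, so 8, to 25/0.8 = 31.25, so 32 pushes, or (8-1) x 5 = 35 to (32-1) x 5 = 155 minutes. That is one hypothetical regimen. The protocol never states it; insulin is stopped before dosing, so glucose may recover on its own; and subjects may eat after the 90-minute sample. A subject at 65 mg/dL would need only 5/2.0 = 2.5, so 3, to 5/0.8 = 6.25, so 7 pushes on the same assumptions.
- **Failure of item 2.** No shortfall is shown. A push at 44 mg/dL gives 44.4 to 45.3, which can reach the range, and the low target suggests that little glucose is intended.
- **A changed efficacy result.** Step 5 of the working shows none.

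**Conclusion.** The point holds as a minor safety and conduct correction. That the 5-second push does not fit an instruction to maintain and pause follows from the text alone, as does the mismatch between item 3's range and the 30-minute checks. The statement that one item 3 push cannot by itself bring a subject from 45-55 to 70 mg/dL rests on the assumed volumes, but has room to spare: at most about 2 mg/dL, or 6.7 mg/dL on the plasma-only bound, against at least 15 mg/dL. It does not extend to subjects already close to 70 at 45 minutes.

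Harm is bounded by item 1, by the 5-minute checks until 70 mg/dL is reached and by the discretionary checks. What remains is uneven handling between sites, which is possible but not shown, and a descriptive amount of glucose infused that may partly reflect site habit. A per-minute unit may have been lost from the bracket; the document cannot confirm this.

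**What to change.** 1. In Section 7.4.2, state that the approximately 5-minute bedside checks continue while rescue glucose is being given, even at 70 mg/dL or above.
2. In items 2 and 3 of Section 8.2.3.1, replace the 5-second bracket with glucose titrated at each check to the stated range: either a mg/kg/min rate with the existing pause limits, or a bolus repeated at each check and withheld above the limit. The clinical team sets the dose and checks it against both ranges, including the 15-25 mg/dL step from item 2 to item 3. No dose is proposed here.
3. Notify the sites.

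The cost is a wording correction, a site notice and a few extra bedside checks in rescued subjects. No extra subjects or visits are needed, and the analyses do not change.

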8.2.4 Visit 3 (follow-up visit)

Visit 3 will take place on Day 28 + 5 days. The subject does not need to be fasting.

At Visit 3, the following assessments will take place:

- Document all changes in concomitant medication
- Physical examination
- Vital signs
- 12-lead ECG
- Local tolerability
- AEs
- Biochemistry, hematology
- Urine stick pregnancy test (women of childbearing potential only)
- Urinalysis
- Antibodies against dasiglucagon/GlucaGen.

After the follow-up visit the End of Trial form must be completed. Even if a subject is not able to attend the follow-up visit, the End of Trial form, the eCRF Accountability/Affirmation Statement form and the Drug Accountability form must be completed.

9 STATISTICAL METHODS

Before database lock and treatment unmasking, a separate statistical analysis plan (SAP) will be finalized, providing detailed methods for the analyses outlined below. Further analysis details may be added or refined in the SAP.

Any deviations from the planned analyses will be described and justified in the final clinical trial report.

9.1 Determination of sample size

Due to requirements in the size of the safety database, the sample size is set to 78 subjects treated with dasiglucagon 0.6 mg. From phase 2, the median time to an increase of 20 mg/dL of the 0.6 mg dose was approximately 10 minutes. With a 2:1:1 randomization ratio for the three treatments, dasiglucagon 0.6 mg, placebo, and GlucaGen 1 mg, and assuming an exponential time-to-recovery distributions with median times of 10 and at least 20 minutes for dasiglucagon and placebo, respectively, a two-sided log-rank test will be able to detect a difference between dasiglucagon and placebo with 90% power with a follow-up time of 45 minutes at a 5% significance level with 78 subjects treated with dasiglucagon and 39 subjects with placebo. The median time-to-recovery for placebo is expected to be longer than 20 minutes, which means that the power will be greater than 90%.

